#### CONFIDENTIAL

The protocol for measuring JL is referenced in Appendix A. Stability, anterior knee pain and the functional component of the KSS will be evaluated with respect to JL.

## 1.2 Study Device

The Triathlon TS Total Knee System has been developed as platform knee technology for Stryker Orthopaedics. The Triathlon TS Total Knee System, cleared for use under FDA 510(k) K072221, includes femoral components fabricated from cast cobalt-chromium-molybdenum alloy, distal and posterior femoral augments, fluted stems, stem extenders, offset adapters, tibial inserts fabricated from ultra high molecular weight polyethylene (UHMWPE) and a patellar component also made from UHMWPE. When mated with the Triathlon TS Universal Tibial Baseplate fabricated from cast cobalt-chrome-molybdenum alloy and tibial augments, these parts provide a total stabilizing knee replacement. The Triathlon TS Total Knee System features an anatomic radius and shortened posterior condyles. These features may allow patients to achieve a greater range of motion (ROM) and greater stability throughout their ROM. Data in support of these marketing claims will be collected in the Triathlon TS Outcomes Study.

## 1.3 Preclinical Data

The following bench tests were conducted on the Triathlon TS Total Knee System components:

Description of the test	Report ID	
Static Shear	– RD-06-122	
Femoral Stem Boss Fatigue	– RD-06-127	
Femur Fatigue	– RD-06-126	
Single Axis Fatigue	– RD-06-123	
Varus/Valgus Constraint	– RD-06-121	
Multi Axis Fatigue	– RD-06-120	
Fluted Stem Fatigue	– RD-06-119	
Range of Constraint	– RD-06-124 and RD-06-12	25

Copies of all test reports are available at Stryker Orthopaedics.

## 1.4 Clinical Data to Date

This study is the first prospective data collection on the Triathlon TS Total Knee System. To date, early data from this study have been presented at the 2012 meetings of the International

### CONFIDENTIAL

Congress for Joint Reconstruction and the Southern Orthopaedic Association. The abstract is summarized below.

Title	Authors	Summary	
Anatomic Boss Position	[name]; [name];	Among 83 cases enrolled at 5	
Decreases the Need for	[name]; [name],	sites, 90.4% did not require a	
Offset in Revision Total Knee	[name] and [name]	femoral offset; this is in	
Arthroplasty		contrast to previous reports	
		that femoral offset adapters	
		were needed in 55.4% of	
		cases to achieve optimal joint	
		line reconstruction. The	
		authors concluded that the	
		design of this system	
		inherently reduced the need	
		for use of the offset adapter in	
		the majority of cases due to	
		the anatomic boss position.	

# 2 Study Objectives

## 2.1 Efficacy

## 2.1.1 Primary

The primary objective of this study will be to evaluate the change in outcomes from the preoperative time point to 2 years postoperative in cases implanted with the Triathlon TS Total Knee System, with regard to both components of the KSS. The change seen from preoperative to postoperative time points will be evaluated within the Triathlon TS group and will also be compared to published revision TKR data. It is expected that the change in the Triathlon TS group is non-inferior, or superior, to the published changes reported.

### CONFIDENTIAL

### 2.1.2 Secondary

The secondary objectives of this study will be to evaluate the effect of JL restoration on revision TKR with specific reference to effect on postoperative stability, anterior knee pain and functional performance at 2 and 5 years postoperatively. It is expected that the Triathlon® TS group with JL elevation > 5 mm is non-inferior to the Triathlon TS group with JL elevation  $\leq$  5 mm.

All outcomes other than the change in KSS, already analyzed as the primary objective, will be analyzed from preoperative to 1, 2 and 5 years postoperatively.

Additionally, the long-term performance of the Triathlon TS Total Knee System for revision TKR will be evaluated with regard to radiographic stability, revision rate and complications when reviewed against published data.

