### CONFIDENTIAL

	Primary:
	• To evaluate the change in outcomes from the preoperative time point to 2 years postoperative in cases implanted with the Triathlon TS Total Knee System, with regard to both components of the KSS.
	Secondary:
Objectives	
 
To evaluate the effect of JL restoration on postoperative stability, anterior knee pain and functional performance. A subset of revision TKR cases will be analyzed by comparing between two groups:
 

	
 
Cases with JL restoration > 5 mm and cases with JL restoration ≤ 5 mm
 

	
 
To evaluate the change between preoperative and postoperative outcomes other than the KSS for the Triathlon TS Total Knee System group.
 

	
 
To review radiographic stability, revision rates and complications for those implanted with the Triathlon TS Total Knee System.
 

Number of Subjects	181 cases implanted with the Triathlon TS Total Knee System as required under this protocol

	Inclusions:
	
 
A. Patient has signed an IRB approved, study specific Informed Patient Consent Form.
 
B. Patient is a male or non-pregnant female age 18 years or older at time of study device implantation.
 
C. Patient is a candidate for revision of all femoral and tibial components of a total knee replacement.
 
D. Patient is willing and able to comply with postoperative scheduled clinical and radiographic evaluations and
 

	rehabilitation.
Diagnosis and Main	Exclusions:
Inclusion/Exclusion	
Criteria	E. Patient has a Body Mass Index (BMI) > 40.
	F. Patient has an active or suspected latent infection in or about
	the affected knee joint at time of study device implantation.
	G. Patient has a neuromuscular or neurosensory deficiency, which
	limits the ability to evaluate the safety and efficacy of the device.
	H. Patient is diagnosed with a systemic disease (e.g. Lupus
	Erythematosus) or a metabolic disorder (e.g. Paget's Disease)
	leading to progressive bone deterioration.
	I. Patient is immunologically suppressed or receiving steroids in
	excess of normal physiological requirements (e.g. > 30 days).
	J. Patient has a failed unicondylar knee prosthesis.
	K. Patient has a known sensitivity to device materials.
	L. Patient is a prisoner.

	Triathlon TS Total Knee System

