## Primary:

	A one-sided 95% confidence interval of the total KSS change from preoperative to 2 years postoperative (2 years - preoperative) will be computed at 2 years postoperative. For the non-inferiority comparison, the lower bound of this confidence interval will be compared with 63 points (10% worse than the expected improvement). For the superiority comparison, the lower bound of this confidence interval will be compared with 70 points (the expected improvement).
Statistical Methodology	Secondary:
	An independent group t-test or a nonparametric test will be used to
	compare the secondary numerical parameters (e.g. KSS, HSS, KOOS)
	between the JL restoration subgroups at 1, 2 and 5 years
	postoperative; and a Chi-square test or Fisher's exact test will be used
	to compare the secondary categorical parameters (e.g. postoperative
	stability, anterior knee pain and functional performance) between the
	subgroups. In addition, a paired t-test or Wilcoxon rank sum test will be
	used to compare the change in outcomes other than the KSS from
	preoperative to 1, 2 and 5 years postoperative within the Triathlon TS
	Total Knee System group. The radiographic stability rates, adverse
	event (AE) rates and revision rates with 95% confidence intervals will
	be presented in tables.

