### CONFIDENTIAL

Page 8

In addition to improving patient outcomes, one of the challenges in revision TKR is restoration of the JL. Improper positioning of the JL has been shown to lead not only to instability but also to an increased incidence of anterior knee pain and decreased flexion. Malposition may also lead to patellar infera and posterior soft tissue impingement by the femoral component. Mason et al., in a study of six cadaver knees, investigated four anatomic landmarks for locating the JL during revision knee surgery – the medial femoral epicondyle (ME), the fibular head (FH), the tibial tubercle (TT), and the inferior pole of the patella (IPP). In this study, the distance between the ME and the JL showed very small patient-to-patient variability. As a result, it was concluded that the ME is a reliable and reproducible landmark for JL measurements.

Additionally, Mahoney and Kinsey retrospectively reviewed JL restoration and clinical outcomes in 22 consecutive femur revision cases. The authors used specialized instruments and were able to restore JL to within 2 mm of anatomic position in 12 of the 22 knees. Flexion and extension gap balancing and ME referencing were reliable methods of measuring and achieving proper position of the JL.

As a secondary objective, this outcomes study of the Triathlon TS Total Knee System will also examine the effect of JL restoration on a subset of revision TKR cases with a non-replaced contralateral knee at the time of study surgery. The effect will be evaluated by comparing between cases with JL restoration > 5 mm and cases with JL restoration  $\leq$  5 mm. As little as 5 mm of displacement from the JL can cause laxity in midflexion or tightness, even in a gap-balanced knee.

For all cases, at the time of study surgery, surgeons will intraoperatively measure, in millimeters, the distance between the ME and the JL in full extension and in 90° of flexion. This measurement will be taken before removal of the previous implants as well as after implantation of the final Triathlon® TS Total Knee System.

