## 9.1.5 Secondary Efficacy Analysis

A two-sided 0.05 alpha level will be used.

For the secondary efficacy parameters when data is available, comparisons of numerical variables between subgroups (e.g. JL groups) will be made by a paired t-test or Wilcoxon rank sum test; comparisons of categorical variables between subgroups will be made by a Fisher's exact test.

One-way analysis of covariance (ANCOVA) may be used as a supportive analysis to determine if the score change from preoperative is significantly different between the subgroups after adjusting the preoperative covariates (e.g. age, gender, BMI), if appropriate.

The mean score improvement from the preoperative time point within the Triathlon® TS Outcomes Study will be summarized in tables at each nominal visit. A p-value will be presented to determine if the mean score improvement from the preoperative time point is non-zero, if appropriate.

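### Section 9.1.5 names a paired t-test for two independent joint-line groups, and Section 2.1.2 expects a non-inferiority that the planned difference tests cannot show

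*Combined protocol and SAP*

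**What the plan says.** All references are to the combined protocol and SAP.

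- **Objective.** The synopsis (Objectives) states the aim as "To evaluate the effect of JL restoration on postoperative stability, anterior knee pain and functional performance". Section 1.1 describes the method: "The effect will be evaluated by comparing between cases with JL restoration > 5 mm and cases with JL restoration" of 5 mm or less, within the subset of cases whose other knee has not been replaced.
- **Expectation.** Section 2.1.2 adds that the "group with JL elevation > 5 mm is non-inferior to the Triathlon TS group with JL elevation" of 5 mm or less.
- **Operative analysis.** Section 9.1.5 sets the level ("A two-sided 0.05 alpha level will be used") and says that "comparisons of numerical variables between subgroups (e.g. JL groups) will be made by a paired t-test or Wilcoxon rank sum test". Categorical variables get Fisher's exact test. An optional ANCOVA "may be used as a supportive analysis to determine if the score change from preoperative is significantly different between the subgroups".
- **Synopsis (Statistical Methodology).** For numerical outcomes between the JL subgroups: "An independent group t-test or a nonparametric test will be used to" compare them. Categorical outcomes get a chi-square or Fisher's exact test. For change within the study group from before surgery, it goes on: "In addition, a paired t-test or Wilcoxon rank sum test will be" used.

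**The concern.** There are two separate faults.

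First, tests are matched to the wrong data structure. The t-test named in the statistical section for the JL groups needs pairs, and there are none. The rank-based test named in the synopsis for within-case change ignores the pairing that is there. Two parts of one document therefore give different instructions for the same JL comparison, and the analyst must guess which governs.

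Second, stated expectation and planned analysis do not meet. A non-inferiority statement needs a margin and a confidence bound to set against it. Neither is given for JL. A difference test that fails to reject says only that the data did not separate the groups, which in a small subset is likely even when one group is worse. At stake is a secondary statement that more than 5 mm of JL change does no harm, resting on a test that cannot show it.

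**Working it through.** **1. Which test fits which comparison**

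| Comparison | Data structure | Section 9.1.5 | Synopsis |
|---|---|---|---|
| JL >5 mm against JL ≤5 mm | two disjoint sets of cases | paired t-test (does not fit) or rank sum (fits) | independent-group t-test or unspecified nonparametric test (fits) |
| Before surgery against follow-up | same case measured twice | p-value promised, no test named | paired t-test (fits) or rank sum (does not fit) |

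A case falls on one side of the 5 mm cut, so the JL groups share no members and no matching is described. The pairing of methods in 9.1.5 is the one that the synopsis uses for within-case change, which suggests that the phrase was carried across. In neither place do both named tests suit the comparison to which they are attached.

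**2. What a non-inferiority statement would need**

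The primary objective shows the pattern. Section 2.1.1 states an expectation of non-inferiority or superiority. Section 9.1.3 turns it into hypotheses, Section 9.1.4 compares a one-sided 95% lower bound with 63 and then 70, and Section 9.4.2 sizes it. The size reproduces: [35 × (1.645 + 0.842) / 7]² = 154.6 against the stated 154, and 154 / 0.85 = 181.2 against the stated 181.

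For JL only the first step exists. There is no hypothesis, margin, bound or sample size. The 7 points in 9.4.2 is 10% of a published improvement of 70 and serves a single-arm comparison; nothing transfers it to a contrast between two groups inside the study.

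**3. Illustration only: why non-significance would not help**

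This borrows SD 35 and 7 points from 9.4.2 (total Knee Society Score change) and assumes equal groups. The documents give no such inputs for JL.

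- All 154 evaluable cases, 77 per group: SE = 35 × √(1/77 + 1/77) = 5.64. With a true deficit of 7 points, 7 / 5.64 = 1.24, and P(non-significant) ≈ Φ(1.96 − 1.24) − Φ(−1.96 − 1.24) ≈ 0.76 (0.77 by noncentral t).
- Half of them in the subset (assumed), 38 and 39: SE = 7.98, 7 / 7.98 = 0.88, P ≈ 0.86 by either method.
- With an assumed SD of 20, noncentral t gives 0.42 and 0.67.

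The spread reflects the inputs chosen. The endpoints that 2.1.2 names (stability, anterior knee pain, functional performance) are given in the synopsis as examples of categorical parameters, so these figures do not describe them. They show only that a missed deficit is an ordinary outcome of such a test.

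**The case against.** Several counter-arguments have force.

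- **The 2.1.2 sentence is an expectation, not a hypothesis.** Section 2.2 uses the same form of words loosely for adverse event rates. But Section 2.1.1 uses it for the primary objective, and there it is formalised. The status of the JL sentence is therefore open, which is itself a reason to settle it.
- **Difference tests suit the objective of evaluating an effect.** They do. The mismatch is with the added sentence, not with the objective.
- **Section 9.1.5 still offers a usable test.** This stands. The rank sum alternative in the same sentence is valid for independent groups, and the synopsis has the right t-test. A reader might infer that the JL comparison has no valid analysis; the documents do not support that.
- **Nobody plans to claim non-inferiority from a non-significant p-value.** A reader might infer such a plan. No text states one, though none rules it out.
- **Restoration or elevation.** The synopsis and Section 1.1 group cases by JL restoration, Section 2.1.2 by JL elevation, which has a direction. A reader might infer two different groupings. JL measurement is specified in Appendix A, which was not available for this review, so this is a query and not a finding.

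**Conclusion.** The point holds on the text alone. The paired t-test in 9.1.5 cannot be applied to the JL groups and contradicts the synopsis; the rank sum test in the synopsis does not fit within-case change; and no planned JL analysis can establish the non-inferiority expected in 2.1.2. None of this depends on an assumed number.

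Its weight is modest. The test mismatches look like drafting slips. The JL comparison is secondary, in a subset of unstated size. A reader might infer that the study's main non-inferiority claim is also in doubt, but that claim has its own hypotheses, thresholds and sample size and is untouched. The probabilities in the illustration are not estimates for this trial.

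**What to change.** 1. **Section 9.1.5:** for the JL groups, name the independent-group t-test or the Wilcoxon rank sum test.
2. **Synopsis, Statistical Methodology:** for within-case change, name the paired t-test or the Wilcoxon signed-rank test. Carry the same wording into 9.1.5, which names no test for this.
3. **Section 2.1.2:** delete the non-inferiority sentence, or reword it as evaluating the effect of JL restoration.
4. **Section 9.1.5 and synopsis:** report each JL endpoint as a between-group difference, in means or proportions, with a two-sided 95% confidence interval.
5. **Query:** check Appendix A and use one grouping term and definition, including direction, in the synopsis, 1.1 and 2.1.2. The definition is the sponsor's to choose.

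Keeping the sentence and adding a margin would be the alternative. It would need an endpoint, a justified margin, a confidence level and a subset size, none of which is given. As a guide only, carrying over SD 35, 7 points, 80% power and one-sided 0.05 needs 2 × 154.6 ≈ 310 cases per group, against 181 enrolled in all.

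The cost is wording in a few places and a check of Appendix A, with no new data or visits. The downside is that the sponsor gives up a non-inferiority statement, though one that the planned analysis could not support.

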### **Clinical Outcome**

Clinical outcomes will be evaluated via the total KSS, including pain, motion and function, preoperatively and at the 6-week, 1, 2 and 5-year visits.

### Patient Outcomes

Four different tools will be used to assess patient health-related QOL preoperatively and at the 6-month, 1, 2 and 5-year visits.

The SF-36 is a 36 item patient questionnaire that evaluates general health and well being by measuring components of physical and mental health. The KOOS will be used to collect information specific to osteoarthritis outcomes and consists of six areas: symptoms, stiffness, pain, functions of daily living, sports and recreational activities and QOL. The HSS Patella Score incorporates both subjective symptoms and objective data specific to the patellofemoral joint. The LEAS is a tool that has recently been developed and validated to evaluate the level of patient activity.

### Radiographic Outcomes

### CONFIDENTIAL

Radiographs will be taken and collected in the AP, ML, and Merchant (30° of flexion) views for the preoperative, 6-week, 1, 2 and 5-year intervals. See Appendix B for the radiographic technique to be used.

Radiographs will be evaluated by an independent reviewer for radiolucency of all components, and subsidence for the tibial and femoral components of the Triathlon TS Total Knee System. JL measurements will also be taken according to Appendix A.

Patellar component positioning will be assessed to determine the presence of tilt and/or displacement. Parameters for radiographic failures will follow the guidelines that have been set by the Knee Society. The scoring system for each of the three components is determined by measuring the width of the radiolucent lines for each of the zones in millimeters for each of the three components. The total widths are added for each zone for each of the three prostheses. The total produces a numerical score for each component. Failure is defined as a score of 10 or greater, regardless of symptoms. A migrating or shifting prosthesis, with or without the disappearance of radiolucent lines, should be considered as a possible or impending failure regardless of the score.

### Performance Requirements

Radiographic analysis of the femoral component will employ seven zones (Zone 1 – Zone 7) in the ML view; analysis of the tibial component will employ three zones (Zone 1 – Zone 3) in the ML view and seven zones (Zone 1 – Zone 7) in the AP view; analysis of the patellar component will employ five zones (Zone 1 – Zone 5) in the Merchant (30° of flexion) view. Radiolucency in at least 50% of a zone and measuring at least 1 mm in width is defined as radiolucency present.

Subsidence is defined as settling of the prosthetic component in bone, and is related to the distance between fixed bony landmarks on the tibia and the prosthesis. It should be noted that Knee Society guidelines state that direct subsidence without angular movement cannot be detected because there is no reference point.

#### **Surgical Details**

In order to promote efficiency in the operating room, the Triathlon Total Knee Instrumentation was consolidated, color coded and configured in modules that

#### CONFIDENTIAL

correspond to the surgical procedure. To assess efficiency, measures of surgical time will be collected to support future improvements.

JL measurements will also be taken intraoperatively according to Appendix A. Investigators will measure, in millimeters, the distance between the ME and the JL. This measurement will be taken in extension and at 90° of flexion, both before and after implantation of the Triathlon TS Total Knee System.

Intraoperative gap measurements will also be obtained by using lamina spreaders to measure the tibio-femoral distance of the medial and lateral compartments in full extension and at 90° of flexion immediately upon removal of the primary implant and adequate debridement of fibrous tissue down to viable bone. Once the lamina spreaders have been applied within each compartment, a ruler should be utilized against the bone to record the distance between the tibia and femur, in millimeters, if the distance cannot be read directly from the instrument.

If available for intraoperative gap measurements, investigators should utilize a femoral tibial tensor spreader which additionally allows applied force to be read so that consistency is maintained in both extension and flexion. This type of instrument may allow for proper tensing of the medial and lateral ligaments and femoral component rotation, to achieve flexion-extension gap balance.

There are numerous measurements required intraoperatively. Appendix A should be referenced for a full summary on required intraoperative measurements. The majority of intraoperative data required is not standard. Appendix A should be referenced in detail so that all source documentation is reflective of non-standard data points collected. All surgical details needed for data collection can be found in Appendix F, on the Surgical Details Case Report Form (CRF).

